14.0 BIOSTATISTICS

As outlined in Table 1 Section 3, prior trials in patients with recurrent PCNSL have observed PFS6m of 35-45% with conventional chemotherapy regimens. The primary objective of this phase II study is to assess the efficacy of the targeted therapy buparlisib. PFS24w rate of patients receiving buparlisib will be estimated along with a 95% confidence interval. Progression-free survival at 24 weeks (PFS24w) is defined as the percentage of patients that have not developed progression of disease or died without progression at 24 weeks from the start of treatment. All patients will be followed for 6 months.

Twenty-one patients will be entered in this trial with an anticipated accrual rate of 1-2/months. The therapy will be considered worth pursuing if ≥ 12 out of 21 participants are progression free at 6 months (lower bound of the 95% confidence interval exceeds 34%, the approximate PFS24w rate with conventional chemotherapy).

Based on an accrual of 21 participants, two-sided 95% binominal confidence intervals for a range of overall response rate are as follows:

Table 14: Two-sided 95% binominal confidence intervals

Number of participants with overall response:		6	8	10	12	14	16
Point estimate of overall response rate:		29%	38%	48%	57%	67%	76%
Two-sided 95% confidence interval (exact binominal):	lower	11.28%	18.11%	25.71%	34.02%	43.03%	52.83%
	upper	52.18%	61.56%	70.22%	78.18%	85.41%	91.78%

In the unlikely event a patient is lost to follow-up before assessment of the primary endpoint he or she will be considered an event in the analysis of the primary endpoint.

In addition to PFS24w, we will assess progression-free survival at 12 weeks and 48 weeks (PFS12w and PFS48w). PFS12w/PFS48w is defined as the percentage of patients that have not developed progression of disease or died without progression at 3/12 months from the start of treatment. PFS12w and PFS48w rates of patients receiving buparlisib will be estimated along with a 95% confidence interval. The PFS12w will be assessed based on the

MEMORIAL SLOAN-KETTERING CANCER CENTER IRB PROTOCOL

IRB#: 14-177 A(5)

imaging and/or CSF assessment at day 1 cycle 3. PFS24w will be based on the imaging and/or CSF assessment at day 1 cycle 6, and PFS48w on imaging and/or CSF assessment at day 1 cycle 12.

Frequencies of toxicities will be summarized based on the Common Toxicity Criteria version 4.0. Adverse events that occur will be reported for and described in terms of incidence and severity. Objective response rate (defined as proportion of patients who achieve a complete and partial response among all patients) will be estimated along with a 95% confidence interval. For patients who respond to treatment (complete or partial response), duration of response will be calculated from the date of response to the date of progression of disease. Patients still responding at date of last follow-up will be censored. Overall survival will be calculated as the time from the start of treatment to the date of death or last follow-up. Overall survival and duration of response will be calculated using Kaplan-Meier methodology.

Pharmacokinetic parameters including half-life, C_{max} , AUC, volume of distribution, and clearance will be determined using non-compartmental methods via WinNonlin (Pharsight, Mountain View, CA). Standard descriptive statistics (mean, standard deviation, median, range) will be presented on all parameters for both serum and CSF samples.

Mutational abnormalities (mutant or not) will be assessed for the following genes: A20, CARD11, CD79B, PIK3CA, PIK3CD and MYD88. Additionally, the phosphorylation status of the following members of the PI3K pathway will be assessed through immunohistochemical staining (activated or not activated). Both, mutational abnormalities as well as immunohistochemical status will be cross tabulated with patient outcomes such as PFS24w and ORR. Associations will be assessed using Fishers exact test. For patients who receive MR spectroscopy peak values will be described and graphically presented through course of treatment. Perfusion data (ADC value categorized as high versus low) will be correlated with patient outcome if data permit.

The evaluation of NANO will be measured by the distribution of change from baseline in the level of function score for each domain.

It is anticipated that 1-2 patients per month will be accrued to this study and the study will be completed within 2 years. Accrual is limited to 10 patients with SCNSL and 11 patients with PCNSL.

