10.0 EVALUATION DURING TREATMENT/INTERVENTION

10.1 General Requirements

Table 6 describes the required procedures. All procedures may increase in frequency if clinically indicated or oriented following a toxicity/adverse event.

A complete history, vital signs (including blood pressure, pulse, respiratory rate, temperature, weight and height), physical and neurological examination (to include documentation of the patients Karnofsky performance status (Appendix 6) and NANO score as well as a serum pregnancy test for women of childbearing potential will be performed on day 1 (+/- 4 days) of each cycle.

Neuro-imaging (including contrast-enhanced MRI/CT brain and total spine) and/or CSF collection (for patients with CSF disease; through Ommaya or spinal tap; including cytology) will need to be performed on all patients on day 1 cycle 3, and each additional odd numbered cycle (+/- 4 days). Imaging will include only the side of active disease (MRI brain for patients with brain disease; MRI total spine for patients with intraspinal disease; MRI brain and total spine for patients with brain and spine disease as well as leptomeningeal disease) or sides suggested by new neurologic symptoms and signs. All MRI imaging will included MR perfusion . If MRI spectroscopy is additionally performed, we will collect the additional data.

CBC with differential, platelets, sodium, potassium, calcium, AST, ALT, alkaline phosphatase, total bilirubin, fasting plasma glucose, creatinine, will need to be performed at day 1 and day 15 of each cycle and at the end of the treatment (+/- 4 days).

Amylase and lipase need to be assessed at the end of the treatment (+/- 4 days).

Chest X-ray and 12-lead ECG need to be done every other cycle starting at day 1 of cycle 3 (+/- 4 days)

Participants need to complete the PHQ-9 and GAD7 self rating mood scale (see Appendix 6).at day 1 and day 15 of cycle 1 and 2. On each consecutive cycle only on day 1 and at the

**MEMORIAL SLOAN-KETTERING CANCER CENTER
IRB PROTOCOL**

IRB#: 14-177 A(5)

end of treatment (+/- 4 days). Questionnaires can be performed over the phone on Cycle 2 Day 15 by research staff, if the participant is not able to physically attend to clinic.

Table 6: Required Activity Calendar

Tests and procedures	Screening	On trial						
		Prior to Registration	Cycle 1		Subsequent cycles		End of treatment	30-day post drug
			Day 1	Day 15	Day 1	Day 15		
Informed consent	X							
Inclusion/exclusion criteria	X							

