12.8 Progression-free survival (PFS)

Progression-free survival (PFS) is defined as the time from the date of treatment start to the date of the first documented PD or death due to any cause. If a patient is not known to have progressed or died at the date of the analysis cut-off or when he/she receives any further anti-cancer therapy, PFS is censored at the time of the last tumor assessment before the cut-off date and before the anti-cancer therapy date. PFS will be based on the investigator's assessment of MRI, CSF studies and clinical presentation.

PFS will be described using Kaplan-Meier curves with appropriate summary statistics. Additionally, we will report PFS at 12 weeks (PFS12w), PFS at 24 weeks (PFS24w) and at 48 weeks (PFS48w).

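### Section 14 sets the primary endpoint at 24 weeks but the go rule at 6 months, and no rule says how progression found on a slightly late week-24 scan is counted

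*Combined protocol and SAP*

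**What the plan says.** Section 14.0 defines the primary endpoint as the percentage of patients who "have not developed progression of disease or died without progression at 24 weeks from the start of treatment". The decision rule in the same section is worded differently: "The therapy will be considered worth pursuing if ≥ 12 out of 21 participants are progression free at 6 months". The parenthesis attached to that rule goes back to weeks: "lower bound of the 95% confidence interval exceeds 34%, the approximate PFS24w rate with conventional chemotherapy". The historical figure behind it is given in months: "prior trials in patients with recurrent PCNSL have observed PFS6m of 35-45% with conventional chemotherapy regimens". PFS12w and PFS48w are named in weeks but defined as the percentage who "have not developed progression of disease or died without progression at 3/12 months from the start of treatment".

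Section 12.8 ends PFS at "the date of the first documented PD or death due to any cause", so progression carries the date on which it is documented. Section 10.1 schedules imaging and/or CSF assessment "on day 1 cycle 3, and each additional odd numbered cycle (+/- 4 days" as the tolerance. Section 9.1 fixes cycles at 28 days and keeps the count running when drug is held. Section 14.0 bases PFS24w on the assessment at day 1 of cycle 6 and PFS48w on day 1 of cycle 12. Both are even-numbered cycles, for which Section 10.1 and Table 6 schedule no scan.

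**The concern.** A go/no-go decision on 21 patients needs one timepoint and one rule for turning a scan result into a success or a failure. Here the endpoint and the decision rule carry different time labels, and the scan closest to 24 weeks may be done on either side of day 168. The plan does not say whether a patient is classified by the date of progression or by the result of a named visit.

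Two consequences follow. The reported PFS24w and the count used for the decision could differ on the same data. Under by-date classification, a scan done a few days late, though still within its allowed window, could move a patient from failure to success at 24 weeks. If the choice is left open, it can be made after the results are known, when one patient may decide the outcome.

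**Working it through.** **1. The plan's own figure.** Inputs from Section 14.0: n = 21, threshold 12, exact two-sided 95% interval. The Clopper-Pearson lower bound for x of n is the 2.5% quantile of Beta(x, n - x + 1).
- 12/21: 34.02%, as printed in Table 14, which just clears 34%.
- 11/21: 29.78%, which does not.

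So 12 is the smallest passing count, and one patient separates go from no-go.

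**2. Timepoints in days from treatment start.**
- 24 weeks = 24 × 7 = 168.
- 6 calendar months = 365.25/2 = about 182.6 (calendar months are an assumption; the documents do not define a month).
- 48 weeks = 336; 12 calendar months = about 365.

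**3. Scan windows.** Day 1 of cycle c is 28 × (c - 1) days after start, ±4.

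| Cycle | Days after start | Window | Scan scheduled? |
|---|---|---|---|
| 5 | 112 | 108-116 | yes |
| 6 (named for PFS24w) | 140 | 136-144 | no |
| 7 | 168 | 164-172 | yes |
| 9 | 224 | 220-228 | yes |
| 12 (named for PFS48w) | 308 | 304-312 | no |
| 13 | 336 | 332-340 | yes |

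The cycle 7 window straddles 24 weeks and ends before 6 calendar months.

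**4. Classification by documented date.**
- Progression on a scan at days 164-168 fails at both timepoints.
- Progression on a scan at days 169-172 passes at 24 weeks and fails at 6 calendar months.
- No patient can fail at 24 weeks and pass at 6 months, since 6 months is later.

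The cycle 13 scan behaves in the same way: days 337-340 pass at 48 weeks and fail at 12 months. There is no such effect at week 12 (84 days), because no scan window contains it.

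**5. Size if the go rule is read at 24 weeks by date.** Assume exponential PFS with a true 24-week rate of 34%.
- S(16 weeks) = 0.34^(16/24) = 0.487.
- Progressing between the week-16 and week-24 scans: 0.487 - 0.340 = 0.147, or 21 × 0.147 = 3.1 patients.
- Patients changing status = 3.09 × (share of progression found by scan) × (share of scans 1-4 days late).
- Apparent rate = 0.34 + 0.147 × the same two shares.

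Neither share is in the documents, so a range is shown:

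| Scan-detected | Scans late | Patients changing status | Apparent PFS24w | P(≥12 of 21) |
|---|---|---|---|---|
| none | none | 0 | 34.0% | 0.025 |
| 50% | 10% | 0.15 | 34.7% | 0.030 |
| 80% | 25% | 0.62 | 36.9% | 0.048 |
| 80% | 50% | 1.24 | 39.9% | 0.083 |

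**6. Size if the go rule is read at 6 calendar months.** The late-scan patients have already failed by then, so lateness does not inflate the count. Under the same exponential model the rate is 0.34^(182.6/168) = 0.310, which is 21 × (0.340 - 0.310) = about 0.6 patients fewer, and P(≥12 of 21) = 0.011. This treats progression as observed when it occurs. Because the next scan is due only at days 220-228, progression arising between the cycle 7 scan and 6 months would be documented only if clinically evident or fatal. The realistic figure therefore lies between 0.011 and 0.025.

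**The case against.** The strongest reply is that Section 14.0 uses weeks and months as loose synonyms. The go-rule sentence measures its 6-month count against a rate labelled PFS24w, the 12- and 48-week endpoints are described as 3 and 12 months, and six 28-day cycles are exactly 168 days. On that reading there is one landmark and no disagreement between endpoint and decision. This is plausible and may be what was intended, but the plan does not say it, and it leaves the by-date window question untouched.

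A second reply is that Section 14.0 scores each landmark from a named assessment, not from a progression date. If the cycle 7 scan were the named assessment and were scored by its result, progression found there would be a failure on any day of the window and the problem would vanish. That is correct, and it is in effect the fix. But the assessment actually named is cycle 6 day 1, at 140 days, where no scan is scheduled, so the text as written does not provide this protection.

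A third reply is that a Kaplan-Meier PFS24w is not explicitly planned. Section 12.8 describes PFS by Kaplan-Meier and lists the landmark rates additionally, while Section 14.0 treats PFS24w as a proportion. That stands; the point does not depend on a Kaplan-Meier reading.

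A reader might infer that the two timepoints together raise the risk of a false go. The documents do not support this: the inflation in step 5 arises only if the go rule is read at 24 weeks, and then there is a single timepoint. Nor does the scan window lie between the two timepoints; only its last four days do.

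**Conclusion.** The point holds in limited form. Section 14.0 gives its primary endpoint and its only decision rule different time labels, and the plan has no rule for progression found within the window of the landmark scan.

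With calendar months and by-date classification, the two can disagree in one direction only, for progression first documented on days 169-172. With 6 months taken as 24 weeks, there is no disagreement, but scan lateness can push the 24-week rate upward.

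The expected effect ranges from about 0.15 to 1.2 of 21 patients, and P(≥12 of 21) from about 0.03 to 0.08 against 0.025 when the go rule is read at 24 weeks by date. These figures rest on exponential PFS, a true rate of 34%, and assumed shares of scan-detected progression and late scans. The lower end is small. The point matters because the margin at 12/21 is 0.02 percentage points and one patient reverses the decision. The sample size, threshold and interval are unaffected, so this is a clarification worth making before analysis, not a critical flaw.

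**What to change.** In Sections 14.0 and 12.8:

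1. State the go rule and every PFS landmark in weeks only (12, 24, 48).
2. Name the scheduled scan that decides each landmark, reconciling cycles 6 and 12 in Section 14.0 with the odd-cycle schedule. By the 28-day count, week 24 is cycle 7 day 1 and week 48 is cycle 13 day 1. Week 12 (84 days) has no scheduled scan: Section 14.0 names cycle 3 day 1, which is 56 days, and the next scan is at 112 days. The plan should say explicitly what PFS12w then measures.
3. State that progression found on the week-24 or week-48 scan, anywhere in its ±4-day window, counts as a failure at that landmark, both in the binomial count and in any Kaplan-Meier reading.
4. Classify deaths by their actual date, so that a patient with a clean landmark scan who dies after day 168 is not made a 24-week failure.

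The cost is a few sentences. The sample size of 21, the threshold of 12 and the visit schedule do not change. The reported PFS24w may come out slightly lower than under by-date counting.

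### Section 14 reads PFS12w, PFS24w and PFS48w at day 1 of cycles 3, 6 and 12, which is weeks 8, 20 and 44; no imaging, CSF or response evaluation is scheduled at cycle 6 or 12

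*Combined protocol and SAP*

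**What the plan says.** Section 14.0 contains both a definition and a visit rule for each landmark.

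- **Definition.** PFS24w is the percentage of patients who "have not developed progression of disease or died without progression at 24 weeks from the start of treatment". PFS12w and PFS48w are defined by status "at 3/12 months from the start of treatment".
- **Visit rule.** For the primary endpoint the rule is "PFS24w will be based on the imaging and/or CSF assessment at day 1 cycle 6". The two secondary landmarks are handled in the same way: the 12-week figure is read from the "imaging and/or CSF assessment at day 1 cycle 3", while for the 48-week figure the section puts "PFS48w on imaging and/or CSF assessment at day 1 cycle 12".
- **Decision rule.** The therapy is worth pursuing if at least "12 out of 21 participants are progression free at 6 months", explained as "lower bound of the 95% confidence interval exceeds 34%, the approximate PFS24w rate with conventional chemotherapy".

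The calendar is set elsewhere. Section 9.0 makes a cycle 28 days with no break between cycles, and Section 9.1 keeps the count running while drug is held. Section 10.1 and Table 6 (footnotes 2 to 4) place imaging, CSF collection and response evaluation on day 1 of odd cycles from cycle 3, with a window of 4 days either side, and again at end of treatment. Day 1 of an even cycle has examination, laboratory and other safety items. Section 10.1 allows extra procedures if clinically indicated.

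**The concern.** The visit rule and the definition cannot both be followed. Day 1 of cycle 6 is four weeks before week 24, and the imaging or CSF assessment that Section 14 names there is not on the calendar. Cycle 12 has the same problem.

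PFS24w is the primary endpoint, and it carries the trial's only decision rule: a count out of 21 compared with a fixed 34%, with no control arm. Anyone progression-free at week 24 was also progression-free at week 20, so an early reading moves the count in one direction only, towards declaring the drug worth pursuing. The rule is also sharp. One patient separates a pass from a fail.

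**Working it through.** **The plan's own figure.** The exact (Clopper-Pearson) two-sided 95% lower bound for x of 21 is the 2.5th percentile of Beta(x, 22 − x). For 12/21 it is 34.02%, as in Table 14, and the other Table 14 columns also reproduce. For 11/21 it is 29.78%. So 12 is the smallest count whose lower bound exceeds 34%.

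**Timing.** Inputs are the 28-day cycle (Section 9.0) and the uninterrupted count (Section 9.1). Weeks elapsed at day 1 of cycle n = 28(n − 1)/7 = 4(n − 1).

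| Landmark | Visit named in Section 14 | Weeks elapsed | Shortfall | Imaging/CSF/response scheduled? |
|---|---|---|---|---|
| PFS12w | Cycle 3 day 1 | 4 × 2 = 8 | 4 weeks | Yes |
| PFS24w | Cycle 6 day 1 | 4 × 5 = 20 | 4 weeks | No (even cycle) |
| PFS48w | Cycle 12 day 1 | 4 × 11 = 44 | 4 weeks | No (even cycle) |

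The 4-day window puts cycle 6 day 1 at weeks 19.43 to 20.57, which does not close a 28-day gap. Week 24 is day 1 of cycle 7 (4 × 6) and week 48 is day 1 of cycle 13 (4 × 12). Both are odd cycles with scheduled assessments. Week 12 is day 1 of cycle 4, which has none; the nearest scans are at weeks 8 and 16.

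The *ends* of cycles 3, 6 and 12 are weeks 12, 24 and 48 (4 × 3, 4 × 6, 4 × 12), so a start-of-cycle/end-of-cycle slip is a likely explanation. The text nevertheless says day 1.

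**Effect on the decision rule (illustration).** The documents give no hazard shape. Assume constant hazard and that every event up to the reading date is captured. With true 24-week rate p, the rate at week 20 is p^(20/24), and the chance of passing is the binomial P(X ≥ 12; n = 21).

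| True 24-week rate | Rate at week 20 | P(pass), week 24 | P(pass), week 20 | Ratio |
|---|---|---|---|---|
| 34% (decision benchmark) | 40.7% | 2.5% | 9.6% | 0.0958/0.0249 = 3.8 |
| 35% | 41.7% | 3.1% | 11.3% | 0.1129/0.0313 = 3.6 |
| 45% (top of the historical range in Section 14) | 51.4% | 18.4% | 38.0% | 0.3803/0.1841 = 2.1 |

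The result depends on the hazard shape. At 34%, Weibull shapes 0.7 and 1.3 give a week-20 pass probability of 6.7% and 13.2%. It also depends on the time unit of the benchmark. Six months is 26.1 weeks, so if 34% is a 6-month rate, constant hazard gives 37.1% at week 24 (P = 4.9%) and 43.7% at week 20 (P = 15.4%).

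**The case against.** The strongest reply is that the governing text is clear. Section 2.1 states the objective as PFS at 24 weeks, Section 12.8 runs PFS to the first documented progression or death, and Section 14 itself defines PFS24w at 24 weeks. A scan exists at week 24, and the rule naming cycle 6 cannot be carried out from scheduled imaging or CSF. A sensible analyst would use the definition and get the right answer. This stands in part: the contradiction is certain, but a biased result is only possible. It does not remove the point, because the visit rule is the plan's only instruction on which assessment to use, and two analysts following the text could reach opposite conclusions. The Kaplan-Meier description in Section 12.8 does not settle it either, since the decision rests on a count out of 21.

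A second reply is that the benchmark matters more. At a correctly timed week-24 reading, moving the true rate from 34% to 45% changes the pass probability from 2.5% to 18.4%, more than the timing shift at 34%. That is true, but it is a separate uncertainty and no reason to keep the wrong visit.

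A reader might infer that, with no cycle 6 scan, status would rest on the week-16 scan alone, giving 48.7% and a pass probability of 29% at the 34% anchor. The documents do not support this. Clear clinical worsening and death count as events (Sections 12.2 and 12.8), the cycle 6 visit includes an examination, Table 6 has an end-of-treatment assessment, and extra procedures are allowed. Nor is 29% an upper bound: with 34% taken as a 6-month rate, the same calculation gives 38.7%.

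**Conclusion.** Section 14 is wrong as written and should be corrected before the primary analysis. The timing error needs no assumption: each named visit is four weeks before its landmark, and those for PFS24w and PFS48w have no scheduled imaging, CSF or response evaluation. The direction is also certain. For an analyst who applies the visit rule, the progression-free count stays the same or rises.

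The size is illustrative. With constant hazard and full capture of events to week 20, the chance of passing rises about two- to fourfold for true 24-week rates from 45% down to 34%. A reader might take a three- to fourfold rise as general, but it holds only near the 34% anchor. Nor do the documents show that the trial's result is or will be biased, since following the 24-week definition avoids the problem. No decision rule depends on PFS12w or PFS48w, so their mistiming affects description only.

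**What to change.** In Section 14:

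- Base PFS24w on the cycle 7 day 1 assessment (week 24) and PFS48w on the cycle 13 day 1 assessment (week 48).
- State that progression found at that assessment within its window of 4 days either side, or any earlier progression or death, counts as an event. Without this, progression seen on day 170, inside the window but after day 168, would be open to dispute.
- For PFS12w, state that no scan falls at week 12 (the nearest are weeks 8 and 16) and report the week-12 estimate with that limitation.
- As secondary wording, use 24 weeks in the decision rule and 12 and 48 weeks in the other definitions in place of 6, 3 and 12 months, and note that the historical benchmark comes from 6-month data.

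How to count a patient who stops treatment without progression and has no cycle 7 scan is a separate question. Section 14 covers only a patient "lost to follow-up before assessment of the primary endpoint he or she will be considered an event", and Section 12.8 has its own censoring rule. This fix does not try to settle it.

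The cost is wording in one section. Both assessments are already in Table 6, so patients on the calendar need no new visit or scan. The reported PFS24w may be lower than a week-20 reading would give, by about 7 points under constant hazard at 34% (40.7% − 34.0% = 6.7).

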10.2 Pharmacokinetic analysis and evaluation of study drug penetration into the CSF space

In phase I clinical trials with buparlisib, preliminary PK data showed that buparlisib accumulated ~3 fold in achieving steady state, consistent with an effective half-life of ~ 40 hours. Steady state can be reached after approximately 7-10 days of daily dosing in most participants.

On day 15 of cycle 1, patients will undergo CSF and plasma pharmacokinetic analysis. At day 15, the study drug has reached steady state. Patients with an Ommaya reservoir will undergo taps of their reservoir at 1h, 2h and 4h after drug administration. Patients without an Ommaya reservoir will undergo a single spinal tap at 2h after study drug administration. The patient will have plasma collection in parallel (patients with Ommaya reservoir: plasma collection at 1h, 2h, and 4h post drug administration; patients without Ommaya reservoir: plasma collection at 2h post drug administration. Each draw should be collected at +/- 30 min of each time point. CSF and plasma concentrations of the drug will be measured by liquid chromatography with tandem mass spectrometry to derive a CSF/plasma concentration. Samples will be stored in the [name] laboratory and analyzed at the end of the study.

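### Section 14 lists pharmacokinetic parameters that the day-15 sampling cannot deliver: one 2 h pair, or pairs at 1, 2 and 4 h, against a half-life of about 40 h

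*Combined protocol and SAP*

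**What the plan says.** Section 14.0 names five parameters. After half-life, Cmax and AUC the sentence ends "volume of distribution, and clearance will be determined using non-compartmental methods via WinNonlin". The next sentence says that descriptive statistics "will be presented on all parameters for both serum and CSF samples". No interval is given for AUC. The sentence has no qualifier, although the perfusion analysis in the next paragraph is made conditional on the data allowing it.

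Section 10.2 gives the sampling, all of it on day 15 of cycle 1:

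- No reservoir: "Patients without an Ommaya reservoir will undergo a single spinal tap at 2h after study drug administration", with one parallel plasma sample.
- Reservoir: "Patients with an Ommaya reservoir will undergo taps of their reservoir at 1h, 2h and 4h after drug administration", with parallel plasma samples.
- Timing: "Each draw should be collected at +/- 30 min of each time point".

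Notes 5 and 6 to Table 6 repeat this schedule. There is no pre-dose sample, none after 4 h, and no second PK day. Section 10.2 also reports from phase I that "buparlisib accumulated ~3 fold in achieving steady state", "consistent with an effective half-life of ~ 40 hours". The only output it names is the assay result used "to derive a CSF/plasma concentration". The Section 2.2 objective asks for drug concentrations in serum and CSF.

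**The concern.** A non-compartmental half-life needs a terminal slope, and volume needs that slope as well. At steady state, clearance needs the AUC over the whole dosing interval. A single concentration supplies neither, and three concentrations within 3 h say very little about a 40 h decline.

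If Section 14 were followed literally, half-life, volume and clearance would be reported from reservoir patients only. Many of those values would come from the fitting and not from the drug, and a mean and SD would not show which. Cmax would mix a lone 2 h value with the highest of three. The number of single-sample patients is not fixed in advance: Section 6.1 asks only that patients tolerate lumbar puncture and/or reservoir taps, so it could be anywhere from 0 to 21 of 21. If Section 14 were not followed, the change would be an unexplained departure from the plan.

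**Working it through.** **Inputs from the documents.** Half-life about 40 h and accumulation about 3-fold (Section 10.2); once-daily dosing, interval 24 h (Sections 5.1.6 and 9.0); sampling at 2 h, or at 1, 2 and 4 h, each ±30 min, at steady state (Section 10.2). **Assumed:** absorption rate, assay error and a one-compartment model for blood. The documents give none of these, and no CSF kinetics.

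**1. The plan's own figure.** k = ln 2/40 = 0.01733 per h. Accumulation = 1/(1 − e^(−24k)) = 1/(1 − 0.6598) = 2.94. This agrees with the stated 3-fold, so 40 h is a fair working value.

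**2. No reservoir.** One concentration gives no slope and no area. Half-life, AUC, volume and clearance (four of the five) cannot be computed, and Cmax equals the 2 h value. No assumption is needed.

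**3. Reservoir: span.** 4 − 1 = 3 h; 3/40 = 0.075 of a half-life; 3/24 = 12.5% of the interval. With the ±30 min windows the span is 2 to 4 h, or 0.05 to 0.10 of a half-life. A true 40 h decline lowers the concentration by 1 − e^(−3k) = 5.1% between 1 and 4 h.

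**4. Reservoir: half-life with assay error.** Take the favourable case: absorption complete and a pure 40 h decline. For times 1, 2 and 4 h, Sxx = (16 + 1 + 25)/9 = 4.667, so SE(slope) = SD(log concentration)/√4.667 = SD/2.160.

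- P(rising slope, no half-life) = Φ(−k/SE).
- P(half-life below 20 h) = P(decline steeper than 2k) = Φ(−k/SE), the same value by symmetry.
- P(half-life 20-80 h) = Φ(k/SE) − Φ(−0.5k/SE).

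| Assumed error per sample | SE | Rising | Below 20 h | 20-80 h |
|---|---|---|---|---|
| 2% | 0.0093 | 3% | 3% | 79% |
| 5% | 0.0231 | 23% | 23% | 42% |
| 10% | 0.0462 | 35% | 35% | 22% |
| 15% | 0.0691 | 40% | 40% | 15% |

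The remaining patients get a half-life above 80 h.

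**5. Reservoir: half-life with absorption still under way.** Assume a one-compartment steady-state blood model with no assay error. With absorption rates of 0.5, 1 and 1.5 per h the slope fitted through 1, 2 and 4 h rises, so there is no half-life. At 2, 3 and 4 per h the half-life is 217, 56 and 45 h. Volume (clearance/slope) is 4.8, 1.35 and 1.10 times its true value.

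**6. Reservoir: 24 h AUC and clearance.** The share of AUC0-24 after 4 h, with instantaneous input, is (e^(−4k) − e^(−24k))/(1 − e^(−24k)) = (0.9330 − 0.6598)/0.3402 = 80.3%. With absorption rates from 4 down to 0.5 per h it is 80.7% to 82.7%. A flat profile gives 20/24 = 83.3%. Clearance = dose/AUC0-24 inherits this.

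**7. What the samples do support.** In the same blood model, the trapezoid AUC over 1-4 h is within 0.7% of its true value at every absorption rate from 0.5 to 4 per h. The 2 h concentration is 95-100% of the modelled peak.

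**The case against.** The strongest reply is that little depends on this list. The Section 2.2 objective needs only concentrations, Section 10.2 asks only for the CSF/plasma comparison, and the schedule supplies both. For a single-sample patient the failure would be obvious at analysis. All of that stands, and it limits the point to one paragraph of Section 14.

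Second, Section 14 says AUC without an interval. A 1-4 h AUC needs no extrapolation, can be computed in every fully sampled reservoir patient, and could serve the CSF comparison. This also stands, so a reader who infers that AUC must go altogether goes too far. Clearance is different, because it needs the full 24 h interval.

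Third, AUC0-24 and clearance may come out close to the truth. In the blood model without assay error, where the fitted slope falls (absorption 2, 3 and 4 per h), AUC0-24 is off by +12%, +4% and +2%, and clearance by −11%, −4% and −2%. Heavy extrapolation is therefore not proof of a large error. But where the slope rises there is no valid extrapolation at all, and the reported summary would not separate the two situations.

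Fourth, the 2 h value is near the modelled blood peak, so the Cmax point is mainly one of labelling. That is accepted.

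**Conclusion.** The parameter list in Section 14 cannot be carried out as written. For patients without a reservoir this is certain: four of the five parameters cannot be computed. For reservoir patients, half-life and volume are not supported, because 3 h is 0.075 of the stated half-life. The percentages that illustrate this rest on assumed assay errors of 2-15% and on treating the effective 40 h half-life as the decline between 1 and 4 h. Clearance would rest on a 24 h AUC of which about 80-83% is unobserved. That range belongs to an assumed one-compartment blood model, and no figure is claimed for CSF.

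A reader might infer that the pharmacokinetic objective fails or that the trial's conclusions are affected. The documents do not support that: the Section 2.2 objective is met by the concentrations collected, and the decision rule in Section 14 uses progression-free status only. The correction is worth making because it is specific and nearly free.

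**What to change.** In Section 14 only:

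- Delete half-life, volume of distribution and clearance.
- Replace AUC with *AUC over 1-4 h (reservoir patients only)*, with no extrapolation.
- Replace Cmax with *highest observed concentration at 1, 2 and 4 h (reservoir patients only)*.
- For all patients, summarise the paired 2 h CSF and plasma concentrations and the CSF/plasma ratio, using the mean, SD, median and range already named, separately by CSF source (Ommaya or lumbar).
- For reservoir patients, also show the 1, 2 and 4 h concentrations.
- Use one term for the blood matrix. Sections 2.2 and 14 say serum and Section 10.2 says plasma, and these should be reconciled.

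The cost is a shorter parameter list. No samples or visits are added, and the sampling schedule and the objective stay as they are, apart from aligning the matrix term.
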